questions to determine if a patient is potentially eligible and interested in enrolling in the study. The *Eligibility Screening Form* is a paper form used by study coordinators to collect eligibility information in person from potential study participants who come into the clinic for a reproductive health visit. The form includes a study introduction script, eligibility screening questions to be asked of the patient, and collects eligibility determination data. Data from these forms are entered into the *Recruitment Log* database by study coordinators on an ongoing basis.

Participant Database

The *Participant Database* is an electronic database housed in a *Zoho Creator* application. Data from the paper *Enrollment Form* are entered into the electronic *Participant Database* by study coordinators; data from the 3- and 9-Month *Follow-up Data Collection Forms* are entered into the database by research assistants. Each eligible patient enrolled in the study should have one record in this database for each of the three forms housed here (*Enrollment Form*, *3-Month Data Collection Form*, and *9-Month Data Collection Form*). The paper *Enrollment Form* collects administrative data, participant information on language and gift card preferences, data on adherence to the study procedures, questionnaire completion data, baseline incentive tracking numbers, and any notes on issues/changes to the study protocol. The paper 3- and 9-Month *Data Collection Form* forms are completed by the research assistant at the 3-month and 9-month follow-up data collection points. One form should be completed for each enrolled participant. The forms collect administrative participant information, questionnaire completion data, incentive tracking data, and notes on issues/concerns with the 3-month or 9-month questionnaire administration session.

Wistia video platform

The majority of study participants watch their assigned video on the Wistia online video platform. Wistia collects dosage data on the percent of the video played for each participant. Research staff at PRG download these data regularly to monitor program dosage. Data from the Wistia platform will be used to measure whether participants received the condition to which they were assigned and dosage received.

4) Analysis

a. Outcome measures:

Primary outcome measures

Our primary research questions ask to what extent the offer to watch *Plan A* relative to the offer to watch *The Toxic Life Cycle of a Cigarette* impacts participants' reported: 1) use of LARC; 2) times having sex without a condom; and 3) receipt of STI testing three months after receiving the treatment. We describe below the specific operationalization of each of these three primary outcome measures.

i. LARC Use

LARC use is constructed as a dichotomous variable – participants are either coded as currently using a LARC or not currently using a LARC. Data used to assess the impact of the treatment (*Plan A*) on LARC use are obtained from the following item on the *Participant Questionnaire*, which is administered to both the treatment and control groups at baseline and three months post-baseline.

- *Which of the following methods of prescription birth control are you currently using?*
 - *None: I am not currently using any of these methods*
 - *Oral contraceptives (for example, the pill)*

- *The patch (for example, Ortho Evra)*
- *The shot/injection (for example, Depo-Provera)*
- *The ring (for example, NuvaRing)*
- *The implant (for example, Implanon or Nexplanon)*
- *IUD (for example, ParaGard, Skyla, or Mirena)*

Persons who indicate that they are currently using either *The implant* or *IUD* are considered to be currently using LARC and are coded as 1. Persons who select *None*, *Oral contraceptives*, *The patch*, *The shot/injection*, or *The ring* are considered to not be currently using LARC and are coded as 0.

Plan A will be considered to have a positive impact on LARC use if, as compared to participants who are assigned to the control group, a larger proportion of participants who are offered *Plan A* report using LARC at the three-month follow-up and the difference between groups is statically significant.

ii. Times having sex without a condom

We operationalize times having sex without a condom as a risk outcome; that is, we measure the frequency with which participants engage in the risk behavior of having sex without a condom, rather than the frequency with which they engage in the safe sex practice of using condoms. Constructing the variable in this way allows us to examine the self-reported sexual behaviors of the full analytic sample of participants, regardless as to whether or not they are sexually active.

Specifically, times having sex without a condom is constructed as a continuous variable – the number of times in the past three months a participant *does not* use condoms while engaging in any type of sex.¹⁰ Data used to assess the impact of the treatment (*Plan A*) on condom use are obtained from the following three items on the *Participant Questionnaire*, which is administered to both the treatment and control groups at baseline and three months post-baseline.

- *In the past three months, how many times have you had vaginal sex without using a condom?*
- *In the past three months, how many times have you had oral sex without using a condom?*
- *In the past three months, how many times have you had anal sex without using a condom?*

Persons who indicate that they have not ever had a particular type of sex (vaginal, oral, or anal) or have not had that type of sex in the past three months are coded as having that type of sex without a condom zero times.¹¹ The final outcome measure is calculated by summing individuals' responses to these three items (the number of times they report they did not use condoms during vaginal, oral, and anal sex).

Plan A will be considered to have a positive impact on times having sex without a condom if, as compared to participants who are assigned to the control group, the number of times

¹⁰ *Plan A* is primarily aimed at reducing STI risk through the development of condom and STI knowledge. Since STIs can be transmitted through any type of sexual contact (i.e., vaginal, anal, or oral), our measure of times having sex without condom use is not limited to sexual intercourse but includes all self-reported sexual activity.

¹¹ The *Participant Questionnaire* contains sexual behavior questions that use a three-month recall period. As research has consistently found that memory of behaviors/events decreases over time and accuracy of recall is negatively associated with length of recall period (Clarke et al. 2008; Schwarz and Oyserman 2001), we use items with three-month recall periods to construct our measures of sexual behaviors since these should elicit more accurate responses than a longer recall period (e.g., six-month).

having sex without condoms reported by participants assigned to *Plan A* at the three-month follow-up is larger than the times reported by control participants and the difference between groups is statically significant.

iii. STI Testing

STI testing is constructed as a dichotomous variable – participants are either coded as having been tested for STIs in the past three months or not tested.¹² Data used to assess the impact of the treatment (*Plan A*) on STI testing are obtained from the following two items on the *Participant Questionnaire*, which is administered to both the treatment and control groups at baseline and three months post-baseline.

- The first question asks: *To the best of your knowledge, have you ever been tested for other sexually transmitted infections/diseases (STIs/STDs), such as chlamydia or gonorrhea?*
- If respondents select *Yes* to the first question, they are then asked this second question: *Have you been tested for STIs/STDs other than HIV in the past 3 months?*

Persons who select *Yes* to the second question are coded as 1, indicating that they have been tested for STIs/STDs other than HIV in the past 3 months. Persons who select *No* to the first and/or second questions are considered to not have been tested and coded as 0.

Plan A will be considered to have a positive impact on STI testing if, as compared to participants who are assigned to the control group, a larger proportion of participants who are offered *Plan A* report STI testing at the three-month follow-up and the difference between groups is statically significant.

Secondary outcome measures

Our secondary research questions ask to what extent the offer to watch *Plan A* relative to the offer to watch *The Toxic Life Cycle of a Cigarette* impacts participants' reported: 1) use of dual methods of protection (condom and prescription birth control use) during vaginal sex; and 2) use of other effective contraceptive methods (pill, patch, ring, or Depo-Provera) three months after receiving the treatment. We describe below the specific operationalization of each of these two secondary outcome measures.

i. Use of dual methods of protection

Use of dual methods of protection during vaginal sex is constructed as a proportionate continuous measure – the proportion of number of times in the past three months a participant has used both a condom and prescription birth control out of the total number of times reported having vaginal sex in the past three months.^{13,14} Data used to assess the impact of the treatment (*Plan A*) on dual methods of protection are obtained from the following two items on the *Participant Questionnaire*, which is administered to both the treatment and control groups at baseline and three months post-baseline.

- *In the past three months, how many times have you had vaginal sex?*
- *Please think about how many times you said you had vaginal sex in question 20. Of the times you had vaginal sex, how many times would you say you used*

¹² See footnote **Error! Bookmark not defined.**

¹³ Participants are provided with a box directly above this question, which lists the specific types of prescription birth control to which we are referring. This list includes the following: *birth control pills; the patch (for example, Ortho Evra); the shot (for example, Depo Provera); the ring (for example, NuvaRing); the implant (for example, Implanon or Nexplanon); and IUD (for example, ParaGard, Skyla, or Mirena).*

¹⁴ See footnote **Error! Bookmark not defined.**

dual methods of protections – that is, how many times did you use both a condom and one of the listed methods of prescription birth control at the same time?

Only those participants who report having vaginal sex in the past three months at both baseline and three-month follow-up will be included in analysis. If an individual responds *No* to the question “*Have you ever had vaginal sex?*” or responds *No* to the question “*In the past 3 months, have you had vaginal sex, even once?*”, the individual will be excluded from analysis of this measure. Because of the fact that the mechanism defining the analytic sample for this research question is not random and there are theoretical reasons to believe that treatment assignment may affect inclusion (i.e., individuals who are offered the treatment may be more likely to abstain from sexual activity at follow-up and therefore excluded from the analytic sample) this constitutes an endogenous subgroup.¹⁵

The proportionate measure will be calculated as the number of times of reported dual methods of protection during vaginal sex in the past three months, divided by the number of times of reported vaginal sex in the past three months, with values ranging from 0 to 1.

Plan A will be considered to have a positive impact on use of dual methods of protection if, as compared to participants who are assigned to the control group, participants who are offered *Plan A* report using dual methods of protection more consistently (i.e., a larger proportion of the times they have vaginal sex) at the three-month follow-up and the difference between groups is statically significant.

ii. Use of other effective contraceptive methods

Use of other effective contraceptive methods is constructed as a dichotomous variable – participants are either coded as currently using other effective contraceptive methods or not currently using any contraceptive methods. Data used to assess the impact of the treatment (*Plan A*) on use of other effective contraceptive methods are obtained from the following item on the *Participant Questionnaire*, which is administered to both the treatment and control groups at baseline and three months post-baseline.

- *Which of the following methods of prescription birth control are you currently using?*
 - *None: I am not currently using any of these methods*
 - *Oral contraceptives (for example, the pill)*
 - *The patch (for example, Ortho Evra)*
 - *The shot/injection (for example, Depo-Provera)*
 - *The ring (for example, NuvaRing)*
 - *The implant (for example, Implanon or Nexplanon)*
 - *IUD (for example, ParaGard, Skyla, or Mirena)*

Persons who indicate that they are currently using either *Oral contraceptives*, *The patch*, *The shot/injection*, or *The ring* are considered to be currently using other effective contraceptive methods and are coded as 1. Persons who select *None* are considered to not be currently using other effective contraceptive methods and are coded as 0.

¹⁵Endogenous subgroups are groups of participants that are defined by an outcome measure. The expected balance in observed and unobserved characteristics between treatment and control participants that results from random assignment cannot be guaranteed in such subgroups and thus effect estimates may be subject to bias. Tests of baseline balance will be conducted; if we have reason to believe there is imbalance between treatment and comparison groups for this outcome, we will reduce this to an exploratory research question.

It should be noted that this measure will only be constructed for individuals who select either *None*, *Oral contraceptives*, *The patch*, *The shot/injection*, or *The ring* to the question “Which of the following birth control methods are you currently using?”. If an individual selects *The implant* or *IUD* to this question, the individual will be excluded from analysis of this measure. As such, the subgroup of participants in which we conduct this analysis will be considered an endogenous subgroup (i.e. not inclusive of our full analytic sample) because it is constructed based on a participant’s response to an outcome measure.¹⁶

Plan A will be considered to have a positive impact on use of other effective contraceptive methods if, as compared to participants who are assigned to the control group, a larger proportion of participants who are offered *Plan A* report using other effective contraceptive methods at the three-month follow-up and the difference between groups is statically significant.

- b. **Analytic sample:** In Central California, eight clinics have been recruited to participate in the study. As explained in the *Study Design* section, clinic-based study coordinators review administrative/clinic data for patients with appointments at the study clinics to identify potentially eligible participants.

Potential participants are eligible if they: 1) are female; 2) are between the ages of 18 and 19 years of age; 3) are Hispanic and/or Latina; 4) are not knowingly pregnant or trying to get pregnant; 5) consent/assent to participate; 6) did not enroll in the SpeakOut study between November 2016 to October 2018¹⁷; and 7) are deemed appropriate for the study with regards to physical and mental health by a clinician, clinic staff, or the study coordinator.

After eligibility is determined, participants are randomized into the treatment (*Plan A*) or control (*The Toxic Life Cycle of a Cigarette*) condition according to procedures detailed in subsection 3b. The act of randomization into either the treatment or control arm constitutes the offer to participate in the intervention and is the point at which the individual becomes a participant in the study. The analytic sample is defined as all participants who were randomized into either the treatment or control conditions and who have reported sufficient outcome and covariate data.¹⁸ Missing data procedures are outlined in subsection 4cv below.

- c. **Data cleaning:** Prior to analysis, PRG staff will systematically screen or review the analytic variables (baseline and outcome) to identify invalid, inconsistent, outlying, missing, and unreliable data.¹⁹ New variables are created in which data that are deemed unusable (i.e., invalid

¹⁶ See footnote 15.

¹⁷ See footnote 4.

¹⁸ As outlined in subsection 4cv, our benchmark approach is to impute baseline/covariate data. As such, sufficient baseline/covariate data means all cases where data are not unit missing. We do not anticipate that we will have different analytic samples for our outcomes of interest; data are expected to be missing entirely for any given respondent at any observation point or not. If for whatever reason analytic samples are different for different outcomes, we will assess baseline equivalence separately for each analytic sample.

¹⁹ We propose to document the prevalence of inconsistent and missing data in a descriptives table presented as an appendix in our final impact report. Along with our presentation of sensitivity analyses, we will present tables that present the prevalence of unit and item missing (which result from nonresponse) as well as inconsistent, unreliable, and invalid data for both treatment and control samples. Regarding inconsistencies specifically, for each sexual behavior variable included in our model specifications (which could therefore influence the constitution of the analytic sample) we will include the following: sample size (the number of observations prior to recoding of inconsistencies) and the number of observations that are inconsistent over-time. If paper questionnaires lead to internally inconsistent data, we will also report on this.

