The intervention is offered to females, aged 18 or 19, who self-identify as either Latina or African American, are visiting a participating reproductive health center, have been deemed appropriate for the study by clinic staff with regards to physical and mental health capacity, are not knowingly pregnant and not trying to get pregnant, have not participated in other Office of Adolescent Health-funded Teen Pregnancy Prevention (OAH TPP) programs, consent to participate in the study, and are willing to complete three- and nine-month follow-up questionnaires.

The treatment condition, *Plan A*, is 23-minute video intervention that promotes effective contraceptive use, use of dual methods of protection (condom use and prescription birth control use), and HIV/STI testing. The video aims to develop sexual health intentions, knowledge, and self-efficacy for communicating with providers about different contraceptive options that have been proven effective, such as LARC. The ultimate goal of the video is to influence viewers' uptake of LARC, reduce unprotected sexual activity, and increase receipt of STI testing.

The control (counterfactual) condition, *The Toxic Life Cycle of a Cigarette*, is a 17-minute video that details the negative effects that cigarettes have on the environment and on people who manufacture and use cigarettes. The informational video uses both narration and interviews to educate viewers on the dangers that cigarettes pose. The video includes no sexual or reproductive health content. The videos are delivered to study participants on laptops in a private room or area of participating reproductive health clinics.

- a. **Intervention condition:** The intervention or treatment condition is a 23-minute video called *Plan A*, which was developed by Sentient Research and is based on the entertainment-education model. Entertainment-education is a process of creating and implementing an entertainment program to increase knowledge, change attitudes, and change behaviors among a target audience regarding a social or health issue.² *Plan A* was developed specifically for an 18 to 19-year-old African American or Latina female audience, and delivers messages about the use of effective sexual protection and contraceptive options.

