 - iii.* **Intended program content:** *Plan A* is a theory-guided, video intervention designed to increase LARC use, increase condom use, and encourage HIV/STI testing in 18-19 year-old African American and Latina females. The intervention aims to motivate behavior change by providing viewers with relevant facts about contraceptive and sexual protection options to create awareness, demonstrating risk reduction strategies for unwanted pregnancy and HIV/STIs, and modeling effective communication with sexual partners and health care providers.
 - iv.* **Intended program delivery:** The *Plan A* video is intended to be delivered within a sexual and reproductive health clinic setting immediately prior to a visit with a health care provider. The video is to be viewed in a private or semi-private location on a laptop or tablet. For this study, PRG has contracted with a reproductive health service delivery organization as an implementation partner. PRG and our implementation partner have strategically selected eight clinics in the Central California region, which predominantly serve the target population, as the sites for this study. Study coordinators have been hired, who are staff of the reproductive health service delivery organization, to facilitate delivery of the intervention to study participants who are randomized to the treatment group. All study coordinators have been trained by PRG on the research protocol. This training provides detailed information on how to conduct participant recruitment, eligibility screening, consent/assent, enrollment, and randomization procedures, as well as data collection, entry, and submission procedures.
- b. **Counterfactual condition:** The control condition is a 17-minute video called *The Toxic Life of a Cigarette*. It was also developed with the entertainment-education model in mind, with the purpose of delivering information about the negative effects of cigarettes on the environment and on the people who manufacture and use cigarettes as well as with the purpose of motivating behavior change around tobacco use. The video does not include any sexual or reproductive health content.

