The resulting variable is continuous with values that range from 0 to k , where 0 indicates that a person has not engaged in sex without a condom in the past three months, and k indicates the number of times the person has engaged in sex without a condom (risk behavior) in the past three months.

Note: The analytic sample will include all respondents who have three-month follow-up data. Persons who indicate they have not had sex will be considered to have participated in the risk behavior 0 times (i.e., they did not engage in sex without a condom).

STI testing	
The protective outcome is operationalized as a dichotomous variable indicating whether a person reports having been tested for STIs in the past three months or not having been tested.
 
The measure is calculated from the following item:
 
 • Have you been tested for STIs/STDs other than HIV in the past 3 months? 
A person who selects either Yes is given a value of 1 for the measure. A person who selects No is given a value of 0 for the measure.
 
The resulting variable is dichotomous with values 0 or 1, where 0 indicates a person who has not been tested for STIs/STDs in the past three months and 1 indicates a person who has been tested for STIs/STDs.
 
Note: The analytic sample will include all respondents who have three-month follow-up data.
	Participant Questionnaire	Three-month follow-up (three months after enrollment)
Use of dual methods of protection	
The protective outcome is operationalized as the proportion of times in the past three months a person reports using both a condom and prescription birth control during vaginal sex out of total times reported having vaginal sex.
	Participant Questionnaire	Three-month follow-up (three months after enrollment)

The measure is calculated from the following two items:

- In the past three months, how many times have you had vaginal sex?
- Please think about how many times you said you had vaginal sex in question 20. Of the times you had vaginal sex, how many times would you say you used dual methods of protection – that is, how many times did you use both a condom and one of the listed methods of prescription birth control at the same time?

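### The success rule for the condomless-sex primary outcome points the wrong way: more sex without a condom would count as a positive impact of Plan A

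*SAP*

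**What the plan says.** Section 4a.ii of the SAP introduces the outcome thus: "We operationalize times having sex without a condom as a risk outcome". The score is the plain sum of three questionnaire items, that is, "the number of times they report they did not use condoms during vaginal, oral, and anal sex". Table 1 in Appendix A keeps that polarity: "Persons who indicate they have not had sex will be considered to have participated in the risk behavior 0 times".

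The intended direction appears in three places. Section 2 says the video's ultimate goal includes to "reduce unprotected sexual activity, and increase receipt of STI testing". Section 2a.iii describes the video as "designed to increase LARC use, increase condom use, and encourage HIV/STI testing". Footnote 10 says that it "is primarily aimed at reducing STI risk through the development of condom and STI knowledge".

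The decision rule at the end of section 4a.ii declares a positive impact when the Plan A count "at the three-month follow-up is larger than the times reported by control participants and the difference between groups is statically significant". Footnotes 10 and 11 fall at a page break inside this sentence, but it reads continuously.

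**The concern.** The count is not reversed, so a higher value is worse. A rule that calls a larger Plan A count a positive impact therefore contradicts both the definition of the outcome and the purpose of the intervention.

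This is the only sentence in the SAP that turns a significant result on this primary outcome into a conclusion. If it is followed, a beneficial reduction cannot be reported as success and a significant increase in risk behaviour would be. If it is not followed, the evaluators depart from a published primary criterion, possibly after seeing the data, and have to explain why.

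**Working it through.** **1. Does another part of the SAP set the direction?**

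| Place in the SAP | Bearing on direction |
|---|---|
| 1a, primary question 2 | Asks about impact; no direction |
| 4a.ii, definition | Risk outcome; higher is worse |
| Table 1, Appendix A | 0 means no condomless sex; higher is worse; no success rule |
| 2, 2a.iii, footnote 10 | Aim is less unprotected sex, more condom use, lower STI risk |
| 4f.i, model | T = 1 for Plan A, so β₁ is the adjusted mean for Plan A minus control; two-tailed test, p < .05 |
| 4f.iii, Benjamini-Hochberg | Ranks p-values only; no direction |
| 4a.ii, decision rule | Positive impact if the Plan A count is larger |

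In the model's terms the written rule is β₁ > 0 and significant. The stated aim corresponds to β₁ < 0. Nothing elsewhere overrides the rule.

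**2. Could a positive impact simply mean a positive coefficient?** No. The SAP uses the same label as its success criterion for LARC use, STI testing, dual methods and other effective contraception. All four are protective, so *larger* is correct there. Condomless sex is the only risk-coded outcome of the five, which suggests that the wording was carried over.

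**3. What the reversal does (illustration).**

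Inputs from the SAP: target N = 1,770 and MDES = .12 (Introduction, September 2017 entry); 1:1 allocation (3b), so 885 per arm; two-tailed .05 (4f.i).

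Assumptions, because the SAP gives no figure: all 1,770 analysed; covariate R² of 0 to 0.4; normal approximation; threshold of .05 before the Benjamini-Hochberg step. The SAP does not tie the MDES to this outcome in particular, so .12 SD serves only as a convenient effect size.

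The plan's own figure first. With 80% power assumed, MDES = (1.960 + 0.842) × √(2/885) = 2.802 × 0.0475 = 0.133 without covariates. To reach .12 needs R² = 1 − (0.12/0.1332)² = 0.19. Power, R² and attrition are not stated, so the match of 1,770 to .12 can be neither confirmed nor refuted. The present point does not depend on it.

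Let SE = √((1 − R²) × 2/885) and λ = 0.12/SE.

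- Probability that the written rule declares a positive impact when Plan A truly lowers the count by .12 SD: Φ(−1.960 − λ).
- Probability when Plan A truly raises it by .12 SD: Φ(λ − 1.960).

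| R² | λ | True benefit, rule as written | True harm, rule as written |
|---|---|---|---|
| 0 | 2.52 | 0.0000037 | 0.71 |
| 0.19 | 2.80 | 0.0000009 | 0.80 |
| 0.4 | 3.26 | 0.00000009 | 0.90 |

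With the direction corrected, the last two columns change places. With no true effect, either rule declares a positive impact with probability 0.025.

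If this were the only significant primary outcome, the Benjamini-Hochberg threshold would be .05/3 = .0167, and 0.71, 0.80 and 0.90 would become 0.55, 0.66 and 0.81.

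**The case against.** The best defence is that this is a drafting slip with a clear intended meaning. The same subsection calls the outcome a risk, section 2 gives the goal as reduction, and Table 1 is consistent with both. A careful analyst reading the whole SAP would probably not apply the sentence literally. No estimate depends on it: coding, OLS model, two-tailed p-value and Benjamini-Hochberg ranking are the same either way. Section 4f.i promises to report the model-estimated effects, so the sign would be visible to readers.

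All of that stands, and it limits the error to interpretation. It does not make the sentence right. A prespecified rule exists so that the conclusion does not rest on the analyst's judgement once results are known, and here the only stated rule gives the wrong conclusion.

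The probabilities also deserve the caution urged against them. They rest on an unstated R², full retention and a normal approximation for a skewed count; attrition would lower the 0.71 to 0.90. They show what a reversed rule does, and the contradiction needs none of them.

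**Conclusion.** The concern holds. The written success criterion for one of three primary outcomes is the reverse of what the outcome's definition and the video's stated aim require, and nothing else in the SAP corrects it. This conclusion comes from the text alone and rests on no assumption. Estimates and p-values are unaffected; the declared conclusion on this outcome would be wrong whenever the difference is significant, in either direction. Because the sentence is a primary decision rule, it must be corrected, even though the slip is easy to recognise.

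**What to change.** In the decision rule of section 4a.ii, change *larger* to *smaller* (or *fewer*). Plan A then has a positive impact on this outcome if β₁, Plan A minus control, is below zero and significant under the Benjamini-Hochberg procedure already set out in section 4f.iii. One added sentence saying that a significant β₁ above zero is an unfavourable result would remove any remaining doubt; it is advisable but not essential to the correction.

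Record the change with a date, preferably before the three-month outcomes are analysed. If they have been analysed already, the report should say that the published rule contained a wording error and state which direction was applied.

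The cost is one word, plus the optional sentence and a line in the record of changes. No data, model, sample size or test changes.
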